16.2.6.3 Subject Questionnaire (All randomized Subjects)

Listing 16.2.6.3 (Page 1 of 3)
Subject Questionnaire
All Randomized Subjects

Treatment Sequence	Subject ID	Questions	Assessment Time Point		Treatment	Answer to Question	Start Date	End Date
AB	xxxxxxx	My eye appears healthy	0s 0s 2m 2m	Right Left Right Left	A B A B	2 2 1 1	xxxx-xx-xx xxxx-xx-xx xxxx-xx-xx	xxx-xx-xx xxxx-xx-xx xxxx-xx-xx

. . .

A: , Tetrahydrozoline 0.05% B: e 0.05%, Glycerin 0.40%

C: Tetrahydrozoline 0.05%, Glycerin 0.20%. Hypromellose 0.2%, Polyethylene glycol 400 1.0%

Assessment time point:

Os = Pre-Treatment prior to the first product application (Baseline),

²m = Following the 2-minute ocular Redness Assessment;

¹⁰h = 10 hours after the 1st product application,

¹²h = 12 hours after the 1st product application.

Answer: 1 = Strongly Disagree, 2 = Somewhat Disagree, 3 = Neither Agree or Disagree, 4 = Somewhat Agree, 5 = Strongly Agree, 9 = I don't have an Opinion.

16.2.7.1 **Subjects with Adverse Events (All randomized Subjects)**

Listing 16.2.7.1 (Page 1 of 1) Subjects with Adverse Events All Randomized Subjects

						 				====			
Treatment Sequence				AE TEXT	Preferred Term	 Date/Time Ended	Freq.	Sev.	Outcm	Rel	Action	Med Given Yes/No	Serious Yes/No
AB	XXXXXX	18	W	xxxxxxx	xxxxxxxxx	18NOV2011 18NOV2011	1 1	1 2	1 1	0	1 1	Yes Yes	No No
===	=					 							
A:	,	Tetra	ahydr	ozoline 0	.05%								

e 0.05%, Glycerin 0.40%

C: Tetrahydrozoline 0.05%, Glycerin 0.20%. Hypromellose 0.2%, Polyethylene glycol 400 1.0%

Race: W=WHITE, B=BLACK OR AFRÎCAN AMERICAN, Â=ASIAN, N=NATIVE HAWÂIIAN OR OTHER PACIFIC ISLANDER, AI=AMERICAN INDIAN OR ALASKA NATIVE, O=OTHER

Freq. (Frequency): 1=SINGLE EPISODE, 2=INTERMITTENT

Sev. (Severity): 1=MILD, 2=MODERATE, 3=SEVERE

Outcm (Outcome): 1=RECOVERED/RESOLVED, 2=NOT RECOVERED/NOT RESOLVED, 3=FATAL, 4=RECOVERED/RESOLVED WITH SEQUELAE,

 $5= {\tt RECOVERING/RESOLVING,~96= UNKNOWN}$ Rel. (Relationship to study drug): 0=NOT RELATED, 11=DOUBTFUL, 12=POSSIBLE, 13=PROBABLE, 14=VERY LIKELY

Action (Action taken with investigational product): 1=NOT CHANGED, 2=REDUCED, 3=INTERRUPTED, 4=WITHDRAWN, 5=INCREASED, 96=UNKNOWN, 98=NOT APPLICABLE

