14.2.3 Summary of Subject Questionnaire (Intent-to-treat Subjects)

Table 14.2.3(Page 1 of x)
Summary of Subject Questionnaire
Intent-to-treat Subjects

	Te 0.05%	Tetrahydrozoline 0.05% Glycerin 0.40%	Tetrahydrozoline 0.05% Glycerin 0.20% Hypromellose 0.2% Polyethylene glycol 400 1.0%
Baseline	(N=xx)	(N=xx)	(N=xx)
Q1: My eye appears healthy			
Strongly agree (1)	xx (xx.x%)	xx (xx.x%)	xx (xx.x%)
Somewhat agree (2)	xx (xx.x%)	xx (xx.x%)	xx (xx.x%)
Neither agree or disagree (3)	xx (xx.x%)	xx (xx.x%)	xx (xx.x%)
Somewhat disagree (4)	xx (xx.x%)	xx (xx.x%)	xx (xx.x%)
Strongly disagree (5)	xx (xx.x%)	xx (xx.x%)	xx (xx.x%)
No opinion [1]	xx (xx.x%)	xx (xx.x%)	xx (xx.x%)
ob(=)	(/	(/	(
Strongly agree & Somewhat agree	xx (xx.x%)	xx (xx.x%)	xx (xx.x%)
N	XX	XX	XX
Mean	XX.X	XX.X	XX.X
S.D.	XX.XX	XX.XX	XX.XX
Median	XX.X	XX.X	XX.X
Min-Max	(xx-xx)	(xx-xx)	(xx-xx)
			
Q6: Му еуе жжжжжжжжж			
Strongly agree (1)	xx (xx.x%)	xx (xx.x%)	xx (xx.x%)
Somewhat agree (2)	xx (xx.x%)	xx (xx.x%)	xx (xx.x%)
Neither agree or disagree (3)	xx (xx.x%)	xx (xx.x%)	xx (xx.x%)
Somewhat disagree (4)	xx (xx.x%)	xx (xx.x%)	xx (xx.x%)
Strongly disagree (5)	xx (xx.x%)	xx (xx.x%)	xx (xx.x%)
No opinion [1]	xx (xx.x%)	xx (xx.x%)	xx (xx.x%)
Strongly agree & Somewhat agree	xx (xx.x%)	xx (xx.x%)	xx (xx.x%)
N	xx	xx	xx
Mean	XX.X	XX.X	XX.X
S.D.	XX.XX	XX.XX	XX.XX
Median	XX.X	XX.X	XX.X
Min-Max	(xx-xx)	(xx-xx)	(xx-xx)

^[1] Response of No opinion will not be included in the calculation of mean, S.D., Median, Min and Max.

Table 14.2.3(Page 2 of x) Summary of Subject Questionnaire Intent-to-treat Subjects

2 minutes after 1 st application	Te (N=xx)	Tetrahydrozoline 0.05% Glycerin 0.40% (N=xx)	Tetrahydrozoline 0.05% Glycerin 0.20% Hypromellose 0.2% Polyethylene glycol 400 1.0% (N=xx)
Q1: My eye appears healthy			
Strongly agree (1)	xx (xx.x%)	xx (xx.x%)	xx (xx.x%)
Somewhat agree (2)	xx (xx.x%)	xx (xx.x%)	xx (xx.x%)
Neither agree or disagree (3)	xx (xx.x%)	xx (xx.x%)	xx (xx.x%)
Somewhat disagree (4)	xx (xx.x%)	xx (xx.x%)	xx (xx.x%)
Strongly disagree (5)	xx (xx.x%)	xx (xx.x%)	xx (xx.x%)
No opinion [1]	xx (xx.x%)	xx (xx.x%)	xx (xx.x%)
Strongly agree & Somewhat agree	xx (xx.x%)	xx (xx.x%)	xx (xx.x%)
N	xx	xx	XX
Mean	XX.X	XX.X	XX.X
S.D.	XX.XX	XX.XX	xx.xx
Median	XX.X	XX.X	XX.X
Min-Max	(xx-xx)	(xx-xx)	(xx-xx)
 			
Q7: My eye xxxxxxxxxxx			
Strongly agree (1)	xx (xx.x%)	xx (xx.x%)	xx (xx.x%)
Somewhat agree (2)	xx (xx.x%)	xx (xx.x%)	xx (xx.x%)
Neither agree or disagree (3)	xx (xx.x%)	xx (xx.x%)	xx (xx.x%)

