Somewhat disagree (4)	xx (xx.x%)	xx (xx.x%)	xx (xx.x%)
Strongly disagree (5)	xx (xx.x%)	xx (xx.x%)	xx (xx.x%)
No opinion [1]	xx (xx.x%)	xx (xx.x%)	xx (xx.x%)
Strongly agree & Somewhat agree	xx (xx.x%)	xx (xx.x%)	xx (xx.x%)
N	xx	xx	xx
Mean	XX.X	XX.X	XX.X
S.D.	XX.XX	XX.XX	XX.XX
Median	XX.X	XX.X	XX.X
Min-Max	(xx-xx)	(xx-xx)	(xx-xx)

^[1] Response of No opinion will not be included in the calculation of mean, S.D., Median, Min and Max.

Table 14.2.3(Page 3 of x) Summary of Subject Questionnaire Intent-to-treat Subjects

10 hrs after 1 st application	Te (N=xx)	Tetrahydrozoline 0.05% Glycerin 0.40% (N=xx)	Tetrahydrozoline 0.05% Glycerin 0.20% Hypromellose 0.2% Polyethylene glycol 400 1.0% (N=xx)
Q1: The product feels gentle on my eye			
Strongly agree (1) Somewhat agree (2) Neither agree or disagree (3) Somewhat disagree (4) Strongly disagree (5) No opinion [1]	xx (xx.x%) xx (xx.x%) xx (xx.x%) xx (xx.x%) xx (xx.x%) xx (xx.x%)	xx (xx.x%) xx (xx.x%) xx (xx.x%) xx (xx.x%) xx (xx.x%) xx (xx.x%)	xx (xx.x%) xx (xx.x%) xx (xx.x%) xx (xx.x%) xx (xx.x%) xx (xx.x%)
Strongly agree & Somewhat agree	xx (xx.x%)	xx (xx.x%)	xx (xx.x%)
N Mean S.D. Median Min-Max	xx xx.x xx.xx xx.x (xx-xx)	xx xx.x xx.xx xx.x (xx-xx)	xx xx.x xx.xx xx.x (xx-xx)
Q7: My eye xxxxxxxxxxx			
Strongly agree (1) Somewhat agree (2) Neither agree or disagree (3) Somewhat disagree (4) Strongly disagree (5) No opinion [1]	xx (xx.x%) xx (xx.x%) xx (xx.x%) xx (xx.x%) xx (xx.x%) xx (xx.x%)	xx (xx.x%) xx (xx.x%) xx (xx.x%) xx (xx.x%) xx (xx.x%) xx (xx.x%)	xx (xx.x%) xx (xx.x%) xx (xx.x%) xx (xx.x%) xx (xx.x%) xx (xx.x%)
Strongly agree & Somewhat agree	xx (xx.x%)	xx (xx.x%)	xx (xx.x%)
N Mean S.D. Median Min-Max	xx xx.x xx.xx xx.x (xx-xx)	xx xx.x xx.xx xx.x (xx-xx)	xx xx.x xx.xx xx.x (xx-xx)

^[1] Response of No opinion will not be included in the calculation of mean, S.D., Median, Min and Max.

Table 14.2.3(Page 4 of x) Summary of Subject Questionnaire Intent-to-treat Subjects

12 hrs after 1 st application	Te (N=xx)	Tetrahydrozoline 0.05% Glycerin 0.40% (N=xx)	Tetrahydrozoline 0.05% Glycerin 0.20% Hypromellose 0.2% Polyethylene glycol 400 1.0% (N=xx)
Q1: The product feels gentle on my eye	=======================================		
Strongly agree (1)	xx (xx.x%)	xx (xx.x%)	xx (xx.x%)
Somewhat agree (2)	xx (xx.x%)	xx (xx.x%)	xx (xx.x%)
Neither agree or disagree (3)	xx (xx.x%)	xx (xx.x%)	xx (xx.x%)
Somewhat disagree (4)	xx (xx.x%)	xx (xx.x%)	xx (xx.x%)
Strongly disagree (5)	xx (xx.x%)	xx (xx.x%)	xx (xx.x%)

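### SAP Table 14.2.3 and Listing 16.2.6.3 print opposite answer codes for the same subject questionnaire, and no recode is stated in the readable text

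*SAP*

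**What the plan says.** The subject questionnaire is a secondary endpoint. Protocol section 7 defines it as frequency tabulations at baseline, 2 minutes, 10 hours and 12 hours. SAP section 4.1.2 gives six questions at baseline and seven at each later time.

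Two SAP shells display the answers:

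- **Table 14.2.3** runs from "Strongly agree (1" to "Strongly disagree (5" (closing brackets omitted) at all four times. For each item it shows counts and percentages, a row pooling the two agree answers, and the mean, S.D., median and range of the codes. Its footnote reads "Response of No opinion will not be included in the calculation of mean, S.D., Median, Min and Max".
- **Listing 16.2.6.3** has a single legend: "1 = Strongly Disagree, 2 = Somewhat Disagree, 3 = Neither Agree or Disagree, 4 = Somewhat Agree, 5 = Strongly Agree", followed by "9 = I don't have an Opinion". Its time key covers the same four times, ending at "12 hours after the 1st product application".

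The two displays share an item at baseline and 2 minutes, which the table prints as "Q1: My eye appears healthy". At 10 and 12 hours the table's first item is instead "The product feels gentle on my eye". At those times the overlap therefore rests on the listing's legend covering all times, not on a shared item.

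**The concern.** A recorded 1 means strong agreement in one output and strong disagreement in the other. Unless the data are recoded between the two, following both shells as written mislabels the answers in at least one of them.

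The mistake could go unnoticed. The S.D. does not change, every value stays between 1 and 5, and percentages still add to 100. Range checks would pass.

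At stake is the direction of the consumer-benefit results: the means, medians and ranges and, in the worst case, the frequency tabulations that the protocol names as the endpoint.

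**Working it through.** The plan gives no figure to reproduce, so the check compares the two keys and works out what the reversal does.

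**The keys side by side**

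| Answer | Table 14.2.3 | Listing 16.2.6.3 |
|---|---|---|
| Strongly agree | 1 | 5 |
| Somewhat agree | 2 | 4 |
| Neither | 3 | 3 |
| Somewhat disagree | 4 | 2 |
| Strongly disagree | 5 | 1 |
| No opinion | no code printed | 9 |

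For codes 1 to 5, code' = 6 - code. A mean m becomes 6 - m and a median likewise. The minimum becomes 6 - max and the maximum 6 - min. The S.D. is unchanged.

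**Search for a recode.** None appears in SAP sections 4.1, 4.1.2 or 5, in the readable parts of SAP 6.3, or in the notes to either shell. Protocol 13.5.1 (data computations), Protocol Appendix 2 (the form) and parts of SAP 6.3 are blank in the public copy, so a recode could be stated there. For the same reason the documents do not show which key matches the form.

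**Four possible cases**

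- Case 0: the listing shows raw codes and the table shows recoded values. Both are right, but the recode is not stated in the readable text.
- Case 1: the data follow the table key. Only the listing legend is wrong and no summary statistic changes.
- Case 2: the data follow the listing key and the table counts answers by label. Percentages are right, but means, medians and ranges are reversed against the printed codes.
- Case 3: the data follow the listing key and the table is programmed from its printed codes. The agree and disagree percentages, including the pooled agree row, also swap.

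**Size.** The documents give no response split, so the splits below are assumptions (strongly agree to strongly disagree, no opinion excluded). Eyes per product: 120 subjects x 2 eyes / 3 products = 80, if balanced and all answer (114 x 2 / 3 = 76 if 114 complete).

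For 40/30/15/10/5%: mean = 0.40x1 + 0.30x2 + 0.15x3 + 0.10x4 + 0.05x5 = 2.10, and 6 - 2.10 = 3.90. Pooled agree = 40 + 30 = 70%; swapped, it is 10 + 5 = 15%. The other rows are worked the same way.

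| Assumed split (%) | Mean, table key | Mean, listing key | Median | S.D. | Pooled agree, case 3 | Eyes of 80 |
|---|---|---|---|---|---|---|
| 40/30/15/10/5 | 2.10 | 3.90 | 2 vs 4 | 1.179 | 70% to 15% | 56 to 12 |
| 10/20/30/25/15 | 3.15 | 2.85 | 3 vs 3 | 1.195 | 30% to 40% | 24 to 32 |
| 20/20/20/20/20 | 3.00 | 3.00 | 3 vs 3 | 1.414 | 40% to 40% | 32 to 32 |

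**Reach.** 6 + 3 x 7 = 27 item-by-time blocks, if every item uses the agree/disagree scale. The shell prints only the first and last item at each time.

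**The case against.** The strongest reply is that only a mismatch between two mock-up legends is shown, not an analytic error. The blank sections may contain the recode, and text missing from the public copy cannot be held against the plan. Two of the four cases change no summary statistic, and only case 3 alters the endpoint as the protocol defines it.

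The shells also contain placeholder material. Listings carry 2011 dates, the adverse-event subgroup table has an under-18 row in an adult trial, and the comfort listing shows half-point values that Protocol 11.1.2 does not allow. A listing legend carried over from elsewhere is plausible; that would be case 1. The listing's own dummy answers point weakly the same way. They go from 2 at baseline to 1 at 2 minutes, which is improvement under the table key and worsening under the listing's legend.

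All of this bears on how likely harm is, and it caps the severity. It does not remove the conflict. Both keys are fully legible, and the table repeats its key at four times, so this is not a broken row from PDF reading. Dummy values cannot settle which key is right. Even with a recode stated elsewhere, anyone tracing the listing to the table would find the codes reversed with no note on either output.

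**Conclusion.** The concern holds as a minor inconsistency. That the printed keys are opposite is certain; that no recode exists is not, because some sections are blank. The numerical effect runs from none (cases 0 and 1, or symmetric answers) to large (lopsided answers in case 3), and the sizes above rest on assumed splits. The questionnaire is descriptive, with no between-treatment test in its table shell. Primary efficacy and safety are unaffected.

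**What to change.** Before database lock, by which time Protocol section 13 requires the SAP to be final, compare both shells with the questionnaire and the EDC code list. Then do one of two things:

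- Print one key in both outputs, correcting the shell that disagrees with the code list.
- Keep both keys and state the recode in the SAP and as a note on the outputs: table code = 6 - listing code, for codes 1 to 5 only.

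With the recode, code 9 must be set aside first and kept out of the numeric summaries, because 6 - 9 = -3. In either case, derive the pooled agree row from the reconciled key.

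The cost is one legend correction or one sentence. If the table turns out to be the wrong shell, its labels must be changed in each block at all four times. Data collection and the primary analysis do not change.

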16.2.7.2 Subjects with Serious Adverse Events (All randomized Subjects)

Listing 16.2.7.2 (Page 1 of 1) Subjects with Serious Adverse Events All Randomized Subjects

=======													
Treatment Sequence			AE Race TEXT	Preferred Term	Date/Time Started	Date/Time Ended	Freq.	Sev.	Outcm	Rel		Med Given Se Yes/No	
AB	xxxxxx	18	W xxxxxx	xxxxxxxxxx	13NOV2011 13NOV2011	18NOV2011 18NOV2011	1 1	1 2	1 1	0	1 1	Yes Yes	No No
C: Tetrah Race: W=W NAT Freq. (Fr Sev. (Sev Outcm (Ou	hydrozolin JHITE, B=B LIVE, O=OT requency): rerity): 1 tcome): 1 5	e 0.05 e 0.05 LACK CHER 1=SIN =MILD, =RECOV to st	OR AFRICAN AN AGLE EPISODE, 2=MODERATE, VERED/RESOLVEVERING/RESOLVEVERING/RESOLVEVERING/RESOLVEVERING/RESOLVEVERING/RESOLVEVEVERING/RESOLVETING/RESOLVETING/	0.40% 0.20%. Hypromellose 0.2% ERICAN, A=ASIAN, N=NATIV 2=INTERMITTENT	E HAWĀIIAN OR RESOLVED, 3=FA UL, 12=POSSIBL LANGED, 2=REDU	OTHER PACIF TAL, 4=RECOV E, 13=PROBAB	TC ISLA ERED/RE	SOLVEI VERY I) WITH S	SEQUE	LAE,		

98=NOT APPLICABLE

16.2.7.3 Subjects Withdrawn from Investigational Product due to Adverse Events (All randomized Subjects)

Listing 16.2.7.3 (Page 1 of 1)
Subjects Withdrawn from Investigational Product due to Adverse Events
All Randomized Subjects

Treatment Subje Sequence ID	ct Age AE (Yr) Race TEXT	Preferred Term	Date/Time Started	Date/Time Ended	Freq.	Sev.	Outcm	Rel	Action	Med Given Yes/No	Serious Yes/No
AB xxxxxx	18 W xxxxxxx	xxxxxxxxx		8NOV2011 18NOV2011	1	1 2	1 1	0	1 1	Yes Yes	No No
Race: W=WHITE, NATIVE, O Freq. (Frequenc Sev. (Severity)	·										
Rel. (Relations	5=RECOVERING/RESOL hip to study drug):	VING, 96-UNKNOWN 0=NOT RELATED, 11=DOUBTI	FUL, 12=POSSIBLE	, 13=PROBABI	LE, 14=	VERY I	IKELY				

Rel. (Relationship to study drug): 0=NOT RELATED, 11=DOUBTFUL, 12=POSSIBLE, 13=PROBABLE, 14=VERY LIKELY Action (Action taken with investigational product): 1=NOT CHANGED, 2=REDUCED, 3=INTERRUPTED, 4=WITHDRAWN, 5=INCREASED, 96=UNKNOWN, 98=NOT APPLICABLE

16.2.7.4 Listing of MedDRA Preferred Terms for Adverse Events (All randomized Subjects)

Data Listing 16.2.7.4 (Page 1 of x)
Listing of MedDRA Preferred Terms for Adverse Events
All Randomized Subjects

System Organ Class	Preferred Term	AE Text	Subject ID
SOC1	PT1	xxxxxx	xxxxxxx
SOC2	PT2	xxxxxxx	xxxxxxx
		xxxxxxx	xxxxxxx
	PT3	xxxxxxx	xxxxxxx
	PT4	xxxxxxx	xxxxxxx
		xxxxxx	xxxxxxx
		xxxxxx	**************************************
